**Table 6 - Study window (in days) for safety variables in LTS11210**

Week (Visit)	Target day	Blood hematology Blood liver function	Blood chemistry a /Urinalysis	Vital signs	ECGs	PK/ADA/ Serum IL-6 b sample	ANA/Anti-ds-DNA/ Rheumatoid factor c
Baseline d (-1)							
0 e (1,2 or 1/2)	1						
2 (3)	15	2-21					
4 (4)	29	22-35		2-42		2-56	
6 (5)	43	36-49					
8 (6)	57	50-63	2-70	43-70			
10 (6.1)	71	64-77					
12 (7)	85	78-126	71-126	71-126		57-126	
24 (8)	169	127-210	127-210	127-210		127-210	
36 (9)	253	211-294	211-294	211-294		211-294	
48 (10)	337	295-378	295-378	295-378	2-504	295-378	2-504
60 (11)	421	379-462	379-462	379-462		379-462	
72 (12)	505	463-546	463-546	463-546		463-546	
84 (13)	589	547-630	547-630	547-630		547-630	
96 (14)	673	631-756	631-756	631-756	505-840	631-756	505-840
120 (16)	841	757-924	757-924	757-924		757-924	
144 (18)	1009	925-1092	925-1092	925-1092	841-1176	925-1092	841-1176
168 (20)	1177	1093-1260	1093-1260	1093-1260		1093-1260	
192 (22)	1345	1261-1428	1261-1428	1261-1428	1177-1512	1261-1428	1177-1512
216 (24)	1513	1429-1596	1429-1596	1429-1596		1429-1596	
240 (26)	1681	1597-1764	1597-1764	1597-1764	1513-1764	1597-1764	1513-1764
264 (28)	1849	1765-1932	1765-1932	1765-1932	≥1765	1765-1932	1765-1932
288 (30)	2017	1933-2100	1933-2100	1933-2100		1933-2100	1933-2184
312 (32)	2185	2101-2268	2101-2268	2101-2268		2101-2268	
336 (34)	2353	2269-2436	2269-2436	2269-2436		2269-2436	2185-2520
360 (36)	2521	2437-2604	2437-2604	2437-2604		2437-2604	
384 (38)	2689	2605-2772	2605-2772	2605-2772		2605-2772	2521-2856
408 (40)	2857	2773-2940	2773-2940	2773-2940		2773-2940	
432 (42)	3025	2941-3108	2941-3108	2941-3108		2941-3108	2857-3192
456 (44)	3193	3109-3276	3109-3276	3109-3276		3109-3276	
480 (46)	3361	3277-3444	3277-3444	3277-3444		3277-3444	3193-3486
504 (48)	3529	3445-3570	3445-3570	3445-3570		3445-3570	
516 (49)	3613	≥3571	≥3571	≥3571		≥3571	≥3487

a Lipids profile (metabolism) was also performed at Weeks 4 and 8 (Week 4: 2-42 days, Week 8: 43-70 days)

b Serum IL-6 sample is collected at Weeks 0, 4, 12, 24, 36, and 48 only; ADA at Week 12 (2-126 days) due to no ADA at Week 4.

c Anti-ds-DNA only if ANA titer is >1:160; Rheumatoid factor only at Week 0, 48, 96, 144, 192, 240, and 264 (or EOT).

d Baseline from previous studies

e The value at Week 0 is defined as the last non-missing value in the measurements collected at Visits 1, 2 and/or 1/2, and/or EOT visit in previous studies.

For PK, ADA and Vital signs, the follow-up (ie, 6-week post-treatment) measurement will be defined based on the sample collected at the follow-up Visit 50.

### **2.5.5 Unscheduled visits**

In any efficacy analyses or summaries, unscheduled visit measurements of CRP will be included for computation of the baseline, but not other visits.

Laboratory, vital sign and ECG data from scheduled and unscheduled visits will be used in PCSA analysis no matter if the data are from the central laboratory or local laboratories. For the by-visit summary on the laboratory parameters, only the measurements performed at the central laboratory will be used.

Unscheduled visit measurements of vital signs and ECG will be included in the by-visit summaries using the visit window defined in [Section 2.5.4](#).

### **2.5.6 Pooling of centers for statistical analyses**

Countries are pooled by region: Western countries, South American and Rest of the world. These lists may be updated as the study is ongoing. Countries may be added and non-active countries will be removed. Countries will not be switched from region to region.

- Region 1 (Western countries): Austria , Australia , Belgium , Canada , Czech Republic, Finland, Germany, Greece, Hungary, Italy, Israel, The Netherlands, New Zealand , Norway, Portugal, Spain, Sweden, United Kingdom, USA
- Region 2 (South American): Argentina , Brazil, Chile, Colombia, Ecuador, Guatemala, Mexico, Peru
- Region 3 (Rest of the world): Belarus , China, Egypt, Estonia, India , Lithuania, Malaysia , Philippines , Poland, Romania, Russia, South Africa, South Korea, Ukraine, Taiwan, Thailand, Turkey

### **2.5.7 Statistical technical issues**

None.

### **3 INTERIM ANALYSIS**

This is an open-label study. Interim reports may be prepared for regulatory submissions or other purposes. However, no alpha adjustment is needed for the final CSR.

#### ***Interim reports for BLA submissions (FDA, EU MAA, etc)***

In general, the analyses for these reports will be performed in the overall sarilumab group, and not according to previous treatment prior to enrollment into LTS11210 due to ongoing imbalanced enrollment from previous studies, different previous treatment duration and rescue sarilumab in EFC11072, except the disposition tables and some special safety analyses such as neutropenia. Only selected efficacy and safety analyses will be determined and performed for the interim reports. PK and ADA analyses will be performed on certain cut-off data in each interim report since not all time points are reached by patients or by study design. The analysis of patient reported outcomes may not be performed. However, the full analyses described in this SAP will be performed in the final CSR.

## **4 DATABASE LOCK**

At the time of the initial sarilumab marketing authorization application for the treatment of RA, an interim database (soft) lock will be performed. Additional database snapshots may be performed prior to subsequent marketing authorization applications in major markets, eg. the EU. The final database lock is planned to occur 4 weeks after last patient last visit.

## **5 SOFTWARE DOCUMENTATION**

All summaries and statistical analyses will be generated using SAS Version 9.2 or higher.

## Appendix A Potentially clinically significant abnormalities (PCSA) criteria

CRITERIA for POTENTIALLY CLINICALLY SIGNIFICANT ABNORMALITIES for phase 2/3 studies (oncology excepted) (From QSD-009536 "Analysis and reporting of safety data from clinical trials through the Clinical Study Report"- Version 3 -21-MAY-2014)		
Parameter	PCSA	Comments
Clinical Chemistry		
ALT	By distribution analysis: >3 ULN >5 ULN >10 ULN >20 ULN Additional analysis*: >1 – 1.5 ULN >1.5 – 3 ULN >3 - 5 ULN >5 – 8 ULN > 8 ULN	Enzymes activities must be expressed in ULN, not in IU/L. Concept paper on DILI – FDA draft Guidance Oct 2007. Internal DILI WG Oct 2008. Categories are cumulative. First row is mandatory. Rows following one mentioning zero can be deleted.
AST	By distribution analysis: >3 ULN >5 ULN >10 ULN >20 ULN Additional analysis*: >1 – 1.5 ULN >1.5 – 3 ULN >3 - 5 ULN >5 – 8 ULN > 8 ULN	Enzymes activities must be expressed in ULN, not in IU/L. Concept paper on DILI – FDA draft Guidance Oct 2007. Internal DILI WG Oct 2008. Categories are cumulative First row is mandatory. Rows following one mentioning zero can be deleted.
Alkaline Phosphatase	>1.5 ULN	Enzymes activities must be expressed in ULN, not in IU/L. Concept paper on DILI – FDA draft Guidance Oct 2007. Internal DILI WG Oct 2008.

**CRITERIA for POTENTIALLY CLINICALLY SIGNIFICANT ABNORMALITIES**  
**for phase 2/3 studies (oncology excepted)**  
*(From QSD-009536 "Analysis and reporting of safety data from clinical trials through the Clinical Study Report"-  
Version 3 -21-MAY-2014)*

Parameter	PCSA	Comments
Total Bilirubin	>1.5 ULN >2 ULN	Must be expressed in ULN, not in µmol/L or mg/L. Concept paper on DILI – FDA draft Guidance Oct 2007. Internal DILI WG Oct 2008. Categories are cumulative. First row is mandatory. Rows following one mentioning zero can be deleted.
Conjugated Bilirubin	>35% Total Bilirubin and TBILI>1.5 ULN  Additional analysis*: >1.5 ULN >2 ULN	Conjugated bilirubin dosed on a case-by-case basis. PCSA to be retrieved manually
Unconjugated bilirubin	Additional analysis*: >1.5 ULN >2 ULN	Must be expressed in ULN, not in µmol/L or mg/L. Categories are cumulative.
ALT and Total Bilirubin	ALT>3 ULN and TBILI>2 ULN	Concept paper on DILI – FDA draft Guidance Oct 2007. Internal DILI WG Oct 2008. To be counted within a same treatment phase, whatever the interval between measurement.
CPK**	>3 ULN >10 ULN	FDA Feb 2005. Am J Cardiol April 2006. Categories are cumulative. First row is mandatory. Rows following one mentioning zero can be deleted.
Creatinine	≥150 µmol/L (Adults) ≥30% change from baseline ≥100% change from baseline	Benichou C., 1994.
CLcr (mL/min) (Estimated creatinine clearance based on the Cockcroft-Gault equation)	<15 (end stage renal disease) ≥15 - <30 (severe decrease in GFR) ≥30 - < 60 (moderate decrease in GFR) ≥60 - <90 (mild decrease in GFR) ≥ 90 (normal GFR)	FDA draft Guidance 2010 Pharmacokinetics in patients with impaired renal function-study design, data analysis, and impact on dosing and labeling

**CRITERIA for POTENTIALLY CLINICALLY SIGNIFICANT ABNORMALITIES  
for phase 2/3 studies (oncology excepted)**

*(From QSD-009536 "Analysis and reporting of safety data from clinical trials through the Clinical Study Report"-  
Version 3 -21-MAY-2014)*

Parameter	PCSA	Comments
eGFR** (mL/min/1.73m  )	<15 (end stage renal disease)	FDA draft Guidance 2010
(Estimate of GFR based on an MDRD equation)	≥15 - <30 (severe decrease in GFR) ≥30 - < 60 (moderate decrease in GFR) ≥60 - <90 (mild decrease in GFR) ≥ 90 (normal GFR)	Pharmacokinetics in patients with impaired renal function-study design, data analysis, and impact on dosing and labeling
Uric Acid		Harrison- Principles of internal Medicine 17 th Ed., 2008.
Hyperuricemia	>408 µmol/L	
Hypouricemia	<120 µmol/L	
Blood Urea Nitrogen	≥17 mmol/L	
Chloride	<80 mmol/L >115 mmol/L	
Sodium	≤129 mmol/L ≥160 mmol/L	
Potassium	<3 mmol/L ≥5.5 mmol/L	FDA Feb 2005.
Total Cholesterol	≥7.74 mmol/L ≥6.2 mmol/L*	Threshold for therapeutic intervention.
LDL	≥4.1 mmol/L* ≥4.9 mmol/L	
Triglycerides	≥4.6 mmol/L ≥5.6 mmol/L*	Threshold for therapeutic intervention.
Lipasemia**	≥3 ULN	
Amylasemia**	≥3 ULN	
Glucose		
Hypoglycaemia	≤3.9 mmol/L and <LLN	ADA May 2005.
Hyperglycaemia	≥11.1 mmol/L (unfasted); ≥7 mmol/L (fasted)	ADA Jan 2008.
HbA1c	>8%	
Albumin	≤25 g/L	
CRP	>2 ULN or >10 mg/L (if ULN not provided)	FDA Sept 2005.

**CRITERIA for POTENTIALLY CLINICALLY SIGNIFICANT ABNORMALITIES  
for phase 2/3 studies (oncology excepted)**

*(From QSD-009536 " Analysis and reporting of safety data from clinical trials through the Clinical Study Report"-  
Version 3 –21-MAY-2014)*

Parameter	PCSA	Comments
Hematology		
WBC	<3.0 Giga/L (Non-Black); <2.0 Giga/L (Black) ≥16.0 Giga/L	Increase in WBC: not relevant. To be interpreted only if no differential count available.
Lymphocytes	<0.5 Giga/L* ≥0.5 Giga/L - LLN* >4.0 Giga/L	
Neutrophils	<1.5 Giga/L (Non-Black); <1.0 Giga/L (Black) <1.0 Giga/L*	International Consensus meeting on drug-induced blood cytopenias, 1991. FDA criteria.
Monocytes	>0.7 Giga/L	
Basophils	>0.1 Giga/L	
Eosinophils	>0.5 Giga/L or >ULN (if ULN≥0.5 Giga/L)	Harrison- Principles of internal Medicine 17 th Ed., 2008.
Hemoglobin	≤115 g/L (Male); ≤95 g/L (Female) ≥185 g/L (Male); ≥165 g/L (Female)  Decrease from Baseline ≥20 g/L	Criteria based upon decrease from baseline are more relevant than based on absolute value. Other categories for decrease from baseline can be used (≥30 g/L, ≥40 g/L, ≥50 g/L).
Hematocrit	≤0.37 v/v (Male) ; ≤0.32 v/v (Female) ≥0.55 v/v (Male) ; ≥0.5 v/v (Female)	
RBC	≥6 Tera/L	Unless specifically required for particular drug development, the analysis is redundant with that of Hb.  Otherwise, consider FDA criteria.
Platelets	< 50 Giga/L* ≥ 50 - 100 Giga/L* ≥700 Giga/L	International Consensus meeting on drug-induced blood cytopenias, 1991.

**CRITERIA for POTENTIALLY CLINICALLY SIGNIFICANT ABNORMALITIES  
for phase 2/3 studies (oncology excepted)**

*(From QSD-009536 " Analysis and reporting of safety data from clinical trials through the Clinical Study Report"-  
Version 3 -21-MAY-2014)*

Parameter	PCSA	Comments
Urinalysis		
pH	≤4.6 ≥8	
Vital signs		
HR	≤50 bpm and decrease from baseline ≥20 bpm ≥120 bpm and increase from baseline ≥20 bpm	To be applied for all positions (including missing) except STANDING.
SBP	≤95 mmHg and decrease from baseline ≥20mmHg ≥160 mmHg and increase from baseline ≥20 mmHg	To be applied for all positions (including missing) except STANDING.
DBP	≤45 mmHg and decrease from baseline ≥10 mmHg ≥110 mmHg and increase from baseline ≥10 mmHg	To be applied for all positions (including missing) except STANDING.
Orthostatic Hypotension		
Orthostatic SDB		
Orthostatic DBP	≤-20 mmHg ≤-10 mmHg	
Weight	≥5% increase from baseline ≥5% decrease from baseline	FDA Feb 2007.

**CRITERIA for POTENTIALLY CLINICALLY SIGNIFICANT ABNORMALITIES  
for phase 2/3 studies (oncology excepted)**

*(From QSD-009536 " Analysis and reporting of safety data from clinical trials through the Clinical Study Report"-  
Version 3 –21-MAY-2014)*

Parameter	PCSA	Comments
ECG		Ref.: ICH E14 guidance (2005) and E14 Q&A (2012), and Cardiac Safety Research Consortium White Paper on PR and QRS (Nada et al. Am Heart J. 2013; 165(4) : 489-500)
HR	
<50 bpm <50 bpm and decrease from baseline <math>\geq</math>20 bpm <40 bpm <40 bpm and decrease from baseline <math>\geq</math>20 bpm <30 bpm <30 bpm and decrease from baseline <math>\geq</math>20 bpm
 
>90 bpm >90 bpm and increase from baseline <math>\geq</math>20bpm >100 bpm >100 bpm and increase from baseline <math>\geq</math>20bpm >120 bpm >120 bpm and increase from baseline <math>\geq</math>20 bpm
	
Categories are cumulative
 
Categories are cumulative

PR	
>200 ms >200 ms and increase from baseline <math>\geq</math>25% > 220 ms >220 ms and increase from baseline <math>\geq</math>25% > 240 ms > 240 ms and increase from baseline <math>\geq</math>25%
	Categories are cumulative
QRS	
>110 ms >110 msec and increase from baseline <math>\geq</math>25% >120 ms >120 ms and increase from baseline <math>\geq</math>25%
	Categories are cumulative
QT	>500 ms	
QTc	
Absolute values (ms) >450 ms >480 ms >500 ms Increase from baseline Increase from baseline ]30-60] ms Increase from baseline >60 ms
	
To be applied to any kind of QT correction formula. Absolute values categories are cumulative
 
QTc >480 ms and <math>\Delta</math>QTc>60 ms are the 2 PCSA categories to be identified in individual subjects/patients listings.

---

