### **10.2.4 Liver Function**

Transient, generally mild, elevation of transaminases has been observed with sarilumab. See the Clinical Investigator's Brochure (CIB).

Moreover, the co-administration of MTX or NSAID may represent an additional risk factor for observing signs of hepatotoxicity which is reflected in the American College of Rheumatology

(ACR) guidelines (12). The investigator is recommended to monitor transaminases in any patient receiving MTX but without any defined threshold for transaminases to start reducing MTX dosage which is thus left to the investigator judgement.

Please refer to [Section 10.5.4](#) for LFT abnormalities to be reported as AEPM/AESI with or without immediate notification.

The Sponsor relies on the Investigator's judgement for adapting concomitant medication, including dose reduction of MTX dosage, in case of LFT abnormalities within the guidelines below.

In the present protocol, in order to closely follow LFTs, assessment of ALT, AST, alkaline phosphatase, prothrombin time, albumin, total bilirubin, conjugated bilirubin and unconjugated bilirubin will be performed per specifications on the study flow chart (see [Section 1.2](#)).

- The study drug should be permanently discontinued in case of confirmed ALT > 5 ULN or in case of confirmed ALT > 3 ULN and concomitant total bilirubin > 2 ULN (unless the patient has a documented Gilbert's disease). A complete serological and ultrasonography work-up should be conducted in case of ALT > 5 ULN or ALT > 3 ULN and concomitant bilirubin > 2 ULN (see [Appendix L](#)).
- If ALT  $\geq$  3 ULN and  $\leq$  5 ULN and bilirubin  $\leq$  2 ULN, administration of study drug must be temporarily interrupted, and the study Investigator should immediately contact the patient to arrange for repeat LFTs within 48 hours from the Investigator's awareness of the abnormal LFT results:
  - IMP should be temporarily interrupted until the ALT is below < 3 ULN then restarted **at the dose of 150 mg q2w** at the Investigator's discretion.
  - LFTs should be repeated according to the provided guideline and at a minimum of every 7 days until conditions for resumption of IMP administration are met (see [Appendix L](#)).

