### **11.2.1 List of criteria for definitive treatment discontinuation**

The patients may withdraw from treatment with IMP if they decide to do so, at any time and irrespective of the reason, or this may be the Investigator's decision. All efforts should be made to document the reasons for treatment discontinuation and this should be documented in the e-CRF.

Study drug will be permanently discontinued in case of the following events:

- Confirmed diagnosis of opportunistic infection based on the investigator's assessment following diagnostic workups and expert consultations
- Active tuberculosis:
  - the diagnosis can be made either on symptoms or on a chest radiograph suggestive of active TB. Patients should be referred to appropriate medical specialists and whenever possible, culture confirmation of disease should be obtained and recorded in the e-CRF.
- The patient is at risk through close contact with a person with active TB and the patient refuses to undergo TB evaluation.
- Culture positive for non-tuberculosis mycobacteria
- Symptoms of systemic hypersensitivity or anaphylactic reactions.
- Severe neurologic disease such as demyelinating disease or PML.
- Significant laboratory abnormalities:
  - ALT > 5xULN or ALT > 3xULN with concomitant total bilirubin > 2xULN (unless patient with documented Gilbert's syndrome)
  - neutrophil count < 500/mm^3, or neutrophil count < 1000/mm^3 with evidence of infection

- platelet count  $<50\,000/\text{mm}^3$ , or platelet count  $<100\,000/\text{mm}^3$  with evidence of bleeding (see [Section 10.2](#)).
- Conversion to HIV positive status
- Acute renal failure
- Pregnancy in female participant.
- Use of any biologic DMARDs other than IMP, or use of any JAK inhibitor
- For EFC13752 patients: use of any non-biologic DMARDs
- Any adverse events, per investigator judgment, that may jeopardize the patient safety.

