The duration of the treatment period in the study will be at least 264 weeks, or up to a maximum of 516 weeks (*except in the UK where the duration of treatment will be 264 weeks*) described in Protocol Amendment 9. However, some patients may complete this study with 260 week treatment duration per Protocol Amendment 8 before the approval of Protocol Amendment 9 in their countries. The total maximum duration of study participation for a patient may be up to 523 weeks.

- 1-week screening period if applicable
- 516-week maximum treatment period in LTS11210 (for the earliest patients enrolled in LTS11210 in 2010 if sarilumab is not commercialized by 2020)
- 6-week follow up period as required per protocol

Patients will either enter a 1-week screening period after the EOT visit (Visit 1 in LTS11210) in initial studies (for patients from EFC11072 Part A or Part B1 and ACT11575), or enrol directly into the treatment period (for patients from EFC11072 Part B2, EFC10832, SFY13370, or EFC13752, the EOT visit in the initial study corresponds to the randomization visit, Visit 1/2 in LTS11210).

At Visit 2 or Visit 1/2 (Week 0) after confirmation of eligibility, patients will be administered the first open-label dose of sarilumab at the investigational site and will be observed for 30 minutes for any medical events. At dosing time points occurring outside site visits, sarilumab can be injected by the patients, or by trained caregivers.

Patients will return for the safety follow-up visit 6 weeks after the EOT visit (V49). In case of early treatment discontinuation, patients are required to complete the EOT visit (V49) and to return for the 6-week safety follow-up visit (Visit 50) as well.

The study will be considered completed for a patient at the time he/she completes all the scheduled procedures.

An optional 12-week sub-study aiming to evaluate the usability of pre-filled syringe with safety system (PFS-S) will be conducted in some countries. Patients enrolled in LTS11210 at selected sites in those countries may participate in the PFS-S sub-study from Week 24 of the main study after providing written informed consent for the sub-study. However, patients may continue to participate in the main trial without participating in the PFS-S sub-study if they wish. Full details of the PFS-S sub-study are presented in [Appendix K](#).

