#### **2.4.4 Analyses of safety data**

##### ***General common rules***

All safety analyses will be performed on the safety population as defined in [Section 2.3.2](#), unless otherwise specified, using the following common rules:

- The baseline value for safety parameters is the original baseline from the previous studies.
- The value at Week 0 is the last non~ missing measurement in data collected at scheduled visits: visit1, visit2 and/or visit1/2 in LTS11210 or EOT visit of previous studies prior to first IMP in LTS11210 study design.
- The Potentially Clinically Significant Abnormality (PCSA) values are defined as abnormal values considered medically important by the sponsor according to predefined criteria/thresholds based on literature review and defined by the sponsor for clinical laboratory tests, vital signs and ECG (PCSA version in BTD-009536 version 3, see [Appendix A](#)).
- PCSA criteria will determine which patients had at least one PCSA during the TEAE period, taking into account all evaluations performed during the TEAE period, including non-scheduled or repeated evaluations. The number of all such patients will be the numerator for the on-treatment PCSA percentage.
- The treatment emergent PCSA denominator by group for a given parameter will be based on the number of patients assessed for that given parameter in the TEAE period by treatment received on the safety population.
- For quantitative safety parameters based on central laboratory/reading measurements, descriptive statistics will be used to summarize results and change from baseline values by visit and treatment received. Summaries will include the endpoint value. The endpoint value is commonly defined as the value collected at the same day/time of the last dose of investigational product. If this value is missing, this endpoint value will be the closest one prior to the last dose intake.
- The analysis of the safety variables will be essentially descriptive and no systematic testing is planned.

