### ***Liver function tests***

The liver function tests, namely AST, ALT, alkaline phosphatase and total bilirubin are used to assess possible drug induced liver toxicity. The proportion of patients with PCSA values at any post-baseline visit by baseline status will be displayed by treatment group for each parameter. The proportion of patients with PCSA values at any post baseline visit may be displayed by duration of exposure for each treatment group.

A graph of distribution of peak values of ALT versus peak values of total bilirubin will also be presented. Note that the ALT and Total bilirubin values are presented on a logarithmic scale. The graph will be divided into 4 quadrants with a vertical line corresponding to 3xULN for ALT and a horizontal line corresponding to 2xULN for total bilirubin.

The normalization (to  $\leq 1$  ULN) or return to baseline (in case of baseline is >ULN) of elevated liver function tests will be summarized by categories of elevation (>3 ULN, >5 ULN, >10 ULN, >20 ULN for ALT and AST; >1.5 ULN for ALP; and >1.5 ULN and >2 ULN for total bilirubin), with following categories of normalization: 1) normalized on-treatment; 2) normalized after last dose; 3) last value not normal. The laboratory values measured during the post-study period will be considered in the analysis of normalization. Note that a patient will be counted only under the maximum elevation category.

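### The combined ALT/bilirubin count and the peak-versus-peak plot have no time limit over a 5- to 10-year period, and no planned summary shows how many patients had both elevations together

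*SAP*

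**What the plan says.** The ALT and Total Bilirubin row of SAP Appendix A sets the criterion "ALT>3 ULN and TBILI>2 ULN" with the comment "To be counted within a same treatment phase, whatever the interval between measurement". Appendix A does not say what a treatment phase is in this study.

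The general safety rules in SAP 2.4.4 set the counting window: "PCSA criteria will determine which patients had at least one PCSA during the TEAE period". SAP 2.1.3 defines that period as the treatment and follow-up epochs together, from first dose to last dose plus 60 days, without a break. On its length, SAP 1.1 states: "The duration of the treatment period in the study will be at least 264 weeks, or up to a maximum of 516 weeks". UK patients stop at 264 weeks.

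For the plot, the liver part of SAP 2.4.4.3 states: "A graph of distribution of peak values of ALT versus peak values of total bilirubin will also be presented". Reference lines are drawn at 3 ULN for ALT and 2 ULN for bilirubin. Protocol 13.5.4.2 plans the same plot. Neither text links the two peaks in time.

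The protocol's rule for permanent discontinuation is worded differently. Protocol 10.2.4 requires "confirmed ALT > 3 ULN and concomitant total bilirubin > 2 ULN", and Protocol 11.2.1 lists "ALT > 5xULN or ALT > 3xULN with concomitant total bilirubin > 2xULN". Both exempt documented Gilbert's disease. The Appendix A row contains neither condition.

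**The concern.** A phase-wide pairing rule does little harm when a phase lasts 12 or 24 weeks. Here the phase is the whole extension. A patient with ALT of 3.2 ULN in Year 1 and bilirubin of 2.1 ULN in Year 6 would meet the combined criterion and appear in the upper-right quadrant of the plot. So would a patient with Gilbert's disease who had one bilirubin value above 2 ULN and, at any other time, one ALT value above 3 ULN.

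The opportunity for such pairs grows with follow-up. In a study whose primary objective is long-term safety, a count that rises with duration for this reason alone could be misread as a late effect.

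The report would also show patients who meet the laboratory criterion but properly never met the stopping rule, with no table to explain the difference. Separating concurrent elevations from pairs years apart would be left to review after the data are seen.

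**Working it through.** **Length of the period.** Reproducing the plan's maximum first: 1 + 516 + 6 = 523 weeks, which agrees with SAP 1.1 ("The total maximum duration of study participation for a patient may be up to 523 weeks"). In years, 264 × 7 / 365.25 = 5.06 and 516 × 7 / 365.25 = 9.89.

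**Patients.** The roll-over numbers in SAP 1.3 sum to 243 + 1040 + 7 + 168 + 454 + 111 = 2023.

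**Scheduled liver tests after Week 0** (study flow charts). Weeks 2 to 12 give 6, Weeks 24 to 96 give 7 and Weeks 120 to 264 give 7, so 20 to Week 264. Weeks 288 to 504 add 10, giving 30.

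**Chance pairs, assumption A (rate per draw).** The documents give no elevation rates, so pA (ALT) and pB (bilirubin) are assumed. Draws are treated as independent and everyone is followed throughout.

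- Any interval: 2023 × [1 − (1 − pA)^k] × [1 − (1 − pB)^k]
- Same draw: 2023 × [1 − (1 − pA·pB)^k]

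| pA, pB | k | Any interval | Same draw |
|---|---|---|---|
| 0.5%, 0.1% | 20 | 3.8 | 0.2 |
| 0.5%, 0.1% | 30 | 8.4 | 0.3 |
| 0.3%, 0.05% | 20 | 1.2 | 0.06 |
| 0.3%, 0.05% | 30 | 2.6 | 0.09 |

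Worked example, first row: 1 − 0.995^20 = 0.0954 and 1 − 0.999^20 = 0.0198, so 2023 × 0.0954 × 0.0198 = 3.8.

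**Chance pairs, assumption B (rate per patient).** Suppose 5% to 15% of patients ever exceed 3 ULN for ALT and 0.2% to 2% ever exceed 2 ULN for bilirubin, independently, among 2000. Expected pairs run from 2000 × 0.05 × 0.002 = 0.2 to 2000 × 0.15 × 0.02 = 6.

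**How far apart chance pairs fall.** For two independent times, uniform over T days, P(gap > d) = (1 − d/T)².

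- T = 264 × 7 = 1848 days: 96.8% are more than 30 days apart and 64.4% more than one year apart.
- T = 516 × 7 = 3612 days: 98.4% and 80.8%.

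Over 264 weeks, the 0.2 to 6 pairs of assumption B split into about 0.006 to 0.19 within 30 days and 0.19 to 5.8 beyond. A window of plus or minus 30 days would therefore remove nearly all chance pairs.

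**Direction of the error in these figures.** They are probably too high. Treatment to 516 weeks applies only to the earliest patients, and only where the drug is not commercialised by 2020 (Protocol 6.2). Dropout is ignored. Confirmed ALT above 5 ULN ends treatment (Protocol 10.2.4), and with it the counting window 60 days after the last dose. In the other direction, unscheduled and local laboratory values also enter the PCSA analysis (SAP 2.5.5).

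**The case against.** The row is a screen. A PCSA is by name only potentially significant, safety analysis is descriptive (SAP 2.4.4), and pairing at any interval looks like a deliberate choice for sensitivity. It can over-count, but it cannot lose a patient whose two elevations coincided. This stands, and it is why the row should be kept.

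Liver cases are also captured elsewhere. The same threshold pair is an example of a medically important event in Protocol 10.4, there without a concomitance condition or a Gilbert's exception. ALT increases leading to permanent discontinuation are notified immediately (Protocol 10.5.4). Hepatic disorders are an adverse event of special interest with their own summaries (SAP 2.1.3.1 and 2.4.4.1). Listings flag PCSA values, so timing can be checked patient by patient. This also stands, but these routes depend on investigator reporting or manual review. None gives a pre-specified laboratory count of concurrent elevations.

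An analysis screen need not equal a stopping rule. Agreed: the gap is that the report has no count to set beside that rule.

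A reader might infer from assumption A that the rule inflates the count about 19- to 28-fold. The figures do not support that. Under independence there are no true cases, so the ratio compares chance pairs with chance pairs and says nothing about a count that includes real, correlated elevations.

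**Conclusion.** The point holds as one of analysis definition, of minor to moderate weight. Nothing limits the interval between the two elevations, the counting period is about 5 to 10 years for completers, the plot shares the property, and no planned summary isolates concurrent elevations.

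The number affected is unknown. Under the assumed rates it runs from below 1 to about 8 of roughly 2000 patients (8.4 / 2023 = 0.4% at most). The upper end needs every patient followed to Week 504, which the design does not provide.

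A reader might infer that elevations years apart will be reported as severe liver injury, or that this row is the study's key hepatotoxicity result. The documents say neither. The label is a PCSA, the primary endpoint is the incidence of adverse events (SAP 2.1.3), and the combined row appears only in Appendix A. Nor do the documents show that such pairs will occur. What they show is that, if they occur, no planned table would tell them apart from concurrent elevations.

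**What to change.** Amend SAP Appendix A and SAP 2.4.4.3 as follows:

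- Keep the any-interval row and label it as a screen.
- Define treatment phase for this study, with its start and end.
- Add a row counting patients with both elevations on the same sample or within a pre-specified window on either side, for example plus or minus 30 days. The window should be two-sided, because one that opens only after the ALT value would drop patients whose bilirubin rose first.
- Mark those patients on the peak-versus-peak plot.
- Show the time between the two elevations for every patient flagged by the screen.
- Identify documented Gilbert's disease separately.

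The cost is one extra derivation and a plot annotation, with no new data collection and no change to any clinical rule. Protocol 10.2.4 already calls for prompt repeat liver tests when ALT is 3 to 5 ULN with bilirubin at or below 2 ULN, so nearby values should often exist. The downside is that scheduled liver tests are 24 weeks apart after Week 96 (Portugal and Sweden also test at the dispensing visits between), so a windowed count may miss some true pairs. That is the reason to report it beside the screen and not in its place.
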